3.1.1.1 Clinical Event Committee

An independent external committee (Clinical Event Committee, [CEC]) will be established to adjudicate centrally and in a blinded fashion whether pre-specified criteria for adjudication endpoints are met.

For any events that qualify for adjudication, trial sites will be required to provide in a timely manner clinical documentation such as (but not limited to) electrocardiograms (ECGs), laboratory values, angiography reports, echocardiography reports, Computed Tomography (CT) and/or Magnetic Resonance Imaging (MRI reports), discharge summaries, and autopsy reports to support the external event adjudication. If the CEC requests more data, all efforts must be made by the site to collect all available data to support adjudication.

For reporting of events and exemption from expedited reporting refer to [Section 5.3.7.2](#).

The tasks and responsibilities of the CEC, and the pre-specified criteria for adjudication will be specified in a charter. The CEC will maintain the adjudication results in writing.

3.1.1.2 Hepatic external adjudication

Certain hepatic events will be adjudicated by external independent experts for severity and causal relationship with the trial medication; both in a blinded fashion. Events to be reviewed will be defined in a hepatic charter.

Events may either be defined by abnormal laboratory values and/or relevant adverse events or both.

For qualifying events, relevant source documents generated from any medical evaluations of these events will be requested including laboratory values, histological analysis, reports from ultrasound, CT, MRI, scintigraphy, hospital discharge letters, and medical reports from other physicians. All evaluations will be performed in a blinded fashion. The assessments will be analysed based on empagliflozin data combined from multiple trials (i.e. on project level).

3.1.1.3 Adjudication of ketoacidosis

Events suspected to be metabolic acidosis, ketoacidosis and DKA will be adjudicated by independent external experts in a blinded fashion.

3.2 DISCUSSION OF TRIAL DESIGN, INCLUDING THE CHOICE OF CONTROL GROUP(S)

A variety of medications have been tested in patients with HFrEF with beneficial effect in morbidity and mortality. The aim of this trial is to recruit patients with HFrEF on various HF background therapies to evaluate the long term effect of empagliflozin on CV death and HHF in a real life clinical setting.

Due to its mode of action empagliflozin should be efficacious in treating patients with HF and could provide additional efficacy in combination with any given background therapy.

The placebo-controlled design is considered ethically acceptable on the basis of appropriate criteria for patient discontinuation, ability to change background therapy to maintain, or obtain, sufficient level of hemodynamic control as defined in relevant local and regional guidelines for optimised standard of care.

The double-blind treatment period is planned until the necessary number of events is observed to evaluate efficacy of empagliflozin compared to standard of care. The 30 days follow-up period is considered to be sufficient for assessment of adverse events and efficacy outcomes after stopping trial medication.

Patients should be receiving appropriate care as defined by their physician or practitioner for all cardiovascular conditions according to the prevailing guidelines. This includes, but is not limited to, (if indicated and not contraindicated) aspirin, statins, a diuretic, an inhibitor of the renin-angiotensin system, a beta-blocker and a mineralocorticoid receptor antagonist, each to be given at clinically appropriate doses, and the use of implantable devices like ICD and CRT. This should be conducted in the context of local or regional guidance for primary or secondary CV prevention.

The rationale for dose and dose-interval selection is described in [Section 4.1.2](#).

3.3 SELECTION OF TRIAL POPULATION

An appropriate number of patients will be screened for the trial in approximately 15 countries. Approximately 480 trial centres will participate to ensure that the estimated 2850 patients are randomised to trial medication and complete the trial. Investigators who fail to randomise at least one patient in the first 12 weeks from site initiation may be excluded from further participation. If enrolment is delayed, additional centres may be initiated. The total number of randomised patients may be adapted based on assessment of the blinded event rate. If the accumulated blinded data suggests a slower accrual of primary outcome events over calendar time than originally projected, then the number of patients randomised may be increased up to 4000. Operationally, the recruitment period would be extended and could continue up to 6 months before the target number of events is expected to be achieved. The number of primary outcome events required is not affected by this consideration. For further details refer to [Section 7.7](#).

Clinical trials contribute toward reducing health disparities through improved knowledge about treatment among diverse populations. Greater diversity in clinical trial samples allows for broader generalisation of trial results, increased minority access to trials, improved standards of care, decreased disparities in disease treatment and outcomes, and improved external validity supported by a more representative sample. Greater number of African-Americans as an example suffer from HF and all efforts must be made to have adequate representation of this minority population from the USA [P15-10667]. Each Investigator should develop a recruitment strategy that ensures the recruitment of a representative patient population and takes into consideration gender, race and ethnicity.

According to previous heart failure trials and registries the prevalence of DM amongst patients with HF varies from 25% to 40%. Prevalence of pre-DM is not clearly understood but it is estimated to vary from 15% to 50% [R16-2384, R16-2382]. In a recent large HF outcome trial, 35% of the patients reported to have diabetes and another 15% found to have undiagnosed diabetes and around 27% had pre-diabetes [R16-2383].

Since there is a chance that empagliflozin, as a diabetes drug, when used in CV outcome trials recruits more patients with T2DM, capping on trial level will be used to aim for a similar distribution of patients with DM, pre-DM or no DM as it is expected in the population of patients with the chronic heart failure in real life.

Via IRT it will be ensured that approximately a minimum of 35% of the trial population will be diabetic patients, a minimum of 15% will be prediabetic patients and a minimum of 20% will be non-diabetic patients.

Additionally recruitment to the three categories of DM, pre-DM or no DM will be monitored on regional level. Capping on regional level may be applied to achieve a contribution of each region to each category of diabetes status. DM in this context is defined as screening HbA1c $\geq 6.5\%$, active treatment with antidiabetic medication (for indication of DM) or history of DM. Pre-DM is defined as screening HbA1c $\geq 5.7\%$ and $< 6.5\%$ without the intake of antidiabetic medication (unless taken for a non-DM indication) and no history of DM. Patients with no DM is defined as screening HbA1c $< 5.7\%$ without any intake of antidiabetic medication (unless taken for a non-DM indication) and no history of DM [R16-2261].

Screening of patients for this trial is competitive, i.e. screening for the trial will stop at all centres when a sufficient number of patients have been randomised to trial treatment. Investigators will be notified when screening is complete and will not be allowed to recruit additional patients thereafter. Patients who have completed visit 1 procedures prior to notification of the termination of recruitment will be allowed to be randomised in the trial, if they meet all eligibility criteria. Patient eligibility will be based upon a complete medical history including a physical examination and clinical laboratory tests. Judgment of the clinical relevance of a concomitant disease is at the discretion of the Investigator.

Re-screening and/or re-testing (of assessments) is permitted if approved by Local Clinical Monitor (CML)/Clinical Lead (CL) or delegate. Whilst the information provided below is not

an exhaustive list, it provides some guidance as to when such re-screening and/or re-testing would be considered appropriate.

Re-testing:

Re-testing for eligibility criteria is only to be performed once for a laboratory result which is obviously received beyond stability at the central laboratory or thought to be a spurious result based on previously available laboratory results. The re-test should be carried out as soon as possible so the laboratory test results will be received within the next planned visit windows in order to avoid protocol window violations.

Re-screening:

- Re-screening of the same patient is only allowed once.
- The patient should be declared a screening failure in the electronic Case Report Form (eCRF) and IRT with their original patient number.
- Upon re-screening, the IRT system will allocate a new screening number for the patient
- The patient must be re-consented using the current approved version of the information sheet and consent form.

A log of all patients enrolled into the trial (i.e. who have signed ICF) will be maintained in the ISF at the investigational site irrespective of whether they have been treated with investigational drug or not.

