5.1.2 Secondary endpoints

The key secondary endpoints, which are part of the testing strategy, are the following:

1. Occurrence of adjudicated HHF (first and recurrent)
2. eGFR (CKD-EPI)_{cr} slope of change from baseline

Other secondary endpoints (not part of confirmatory testing hierarchy on trial level) are the following:

- Time to first occurrence of chronic dialysis or renal transplant or sustained* reduction of $\geq 40\%$ eGFR (CKD-EPI)_{cr} or
 - sustained eGFR (CKD-EPI)_{cr} < 15 mL/min/1.73 m² for patients with baseline eGFR ≥ 30 mL/min/1.73 m²
 - sustained eGFR (CKD-EPI)_{cr} < 10 mL/min/1.73 m² for patients with baseline eGFR < 30 mL/min/1.73 m²

* An eGFR (CDK-EPI)_{cr} reduction is considered sustained, if it is determined by two or more consecutive post-baseline central laboratory measurements separated by at least 30 days (first to last of the consecutive eGFR values).

Chronic dialysis is regarded as chronic if the frequency of dialysis is twice or more per week for at least 90 days.

- Time to first adjudicated HHF
- Time to adjudicated CV death
- Time to all-cause mortality
- Time to onset of DM (defined as HbA1c $\geq 6.5\%$ or as diagnosed by the Investigator) in patients with pre-DM defined as no history of DM and no HbA1c ≥ 6.5 before treatment, and a pre-treatment HbA1c value of ≥ 5.7 and < 6.5
- Change from baseline in clinical summary score (HF symptoms and physical limitations domains) of the Kansas City Cardiomyopathy Questionnaire (KCCQ) at week 52
- Occurrence of all-cause hospitalisation (first and recurrent)

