7.3 PLANNED ANALYSES

The primary efficacy analysis will be based on the randomised set (RS), including all randomised patients.

The safety analysis will be based on the treated set (TS), which consists of all patients treated with at least one dose of the trial medication.

For both efficacy and safety analyses, treatment will be evaluated as randomised.

For serum creatinine and values based on upon this measurement such as eGFR, baseline will be defined as the mean of all available measurements from the screening visit until start of randomised trial medication.

Baseline status of DM is defined as:

- DM: any pre-treatment HbA1c above 6.5 or history of DM as entered in the eCRF on the medical history page
- Pre-DM: no history of DM and no HbA1c ≥ 6.5 before treatment and a pre-treatment HbA1c value of ≥ 5.7 and < 6.5
- Non-DM: not meeting criteria of DM or pre-DM above

For all other endpoints, baseline will be defined as the last available measurement before start of randomised trial medication.

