7.6 RANDOMISATION

The trial will be performed as a double-blind design with respect to placebo and empagliflozin. Subjects will be randomised to the trial treatments in a 1:1 ratio. The randomisation will be stratified by the following factors:

- Geographical region (North America, Latin America, Europe, Asia, Other)
- Status of DM at screening :

- no DM (HbA1c < 5.7% without the intake of antidiabetic medication, unless taken for a non-DM indication, and no history of DM) or
 - pre-DM (HbA1c \geq 5.7% and <6.5% without the intake of antidiabetic medication, unless taken for a non-DM indication, and no history of DM) or
 - DM (HbA1c \geq 6.5%, or intake of antidiabetic medication for a DM indication, or history of DM)
- and eGFR (CKD-EPI)cr at screening
 - <60 mL/min/1.73m²
 - \geq 60 mL/min/1.73m²

Patients will be randomised in blocks to double-blind treatment via an IRT system. Approximately equal numbers of patients will be randomised to each treatment group. BI will arrange for the randomisation and the packaging and labelling of trial medication. The randomisation list will be generated using a validated system, which involves a pseudo-random number generator so that the resulting treatment will be both reproducible and non-predictable. The block size will be documented in the Clinical Trial Report (CTR). Access to the codes will be controlled and documented.

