### 9.3 DEFINITION OF DM AT BASELINE

Table 9.3: 1 DM at baseline

Diabetes status at baseline	Definition
T1DM	Patients who fulfil the following: 

- investigator-reported medical history of diabetes on the medical history page

 AND 

- type of diabetes is T1DM

T2DM	Patients who do not have T1DM but fulfil one of the following: 

- investigator-reported medical history of diabetes on the medical history page OR

- any pre-treatment HbA1c value <math>\geq 6.5</math> OR

- stratification via IRT in group of diabetes with either missing assessment of history of diabetes on the medical history page, or no pre-treatment measurement of HbA1c available and investigator reported 'no' for the medical history of diabetes

Table 9.3: 1 DM at baseline (cont.)

Diabetes status at baseline	Definition
Pre-DM	
Patient who fulfil one of the following:
 
 
- investigator reported ‘no’ for the medical history of diabetes on the medical history page AND no pre-treatment HbA1c <math>\geq 6.5</math> and a pre-treatment HbA1c value of <math>\geq 5.7</math> and <math>< 6.5</math>
 
 
OR
 
 
- stratification via IRT in group of pre-diabetes with either 
 
○ missing assessment of history of diabetes on the medical history page and no pre-treatment HbA1c <math>\geq 6.5</math> OR
 
○ no pre-treatment measurement of HbA1c and investigator reported ‘no’ for the medical history of diabetes
 
 
 
 
OR
 
 
- missing assessment of history of diabetes on the medical history page AND all pre-treatment HbA1c <math>< 6.5</math> and a pre-treatment HbA1c value of <math>\geq 5.7</math> and <math>< 6.5</math> and stratification via IRT in group of no diabetes
 

Normal (excluding pre-DM)	Patients not meeting the criteria of DM or pre-DM

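### Protocol 7.3 misplaces an HbA1c of exactly 6.5%, and the analysis definitions of baseline diabetes, unlike the strata and caps, have no criterion for antidiabetic treatment

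*Protocol*

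**What the plan says.** **Caps and strata.** Protocol 3.3 counts as diabetic a patient with screening HbA1c of at least 6.5%, "active treatment with antidiabetic medication (for indication of DM) or history of DM". Protocol 7.6 uses the same rule for the randomisation stratum: HbA1c of at least 6.5%, "or intake of antidiabetic medication for a DM indication, or history of DM". In both sections, pre-diabetes and no diabetes require that no antidiabetic drug is taken, unless for another indication.

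**Protocol 7.3 (analysis).** Diabetes is "any pre-treatment HbA1c above 6.5 or history of DM as entered in the eCRF on the medical history page". Pre-diabetes needs no history, no pre-treatment value of 6.5 or more, and a value from 5.7 to below 6.5. Non-DM is the remainder: "not meeting criteria of DM or pre-DM above".

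**SAP 9.3 (analysis).** Type 2 diabetes is a recorded history, or "any pre-treatment HbA1c value" of 6.5 or more, or a fallback on the IRT stratum. The fallback reads "stratification via IRT in group of diabetes with either missing assessment of history of diabetes on the medical history page", or alternatively applies when no pre-treatment HbA1c exists and history is 'no'. SAP 7.1 says that analyses otherwise use CRF and central laboratory data, not the IVRS stratum.

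**Diabetes onset.** Protocol 5.1.2 defines this endpoint "in patients with pre-DM defined as no history of DM and no HbA1c" of 6.5 or more before treatment, with a pre-treatment value from 5.7 to below 6.5. SAP 7.5.2 takes patients with pre-diabetes at baseline. An onset is an HbA1c of at least 6.5% or a diagnosis by the investigator.

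**The concern.** One patient can be diabetic for randomisation and not diabetic for analysis, by two routes: the boundary value of 6.5% in Protocol 7.3, and treatment for diabetes that the analysis rules do not count. An HbA1c below 6.5% on treatment does not show that diabetes is absent.

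Baseline diabetes status is used in four places:
- It is a three-level covariate in the primary Cox model. SAP 7.4.1 declines a stratified Cox model because the stratification factors are already covariates, but the diabetes covariate does not follow the stratum definition.
- It defines the diabetic versus non-diabetic subgroup, which SAP 6.4 ranks as the most important subgroup analysis. Pre-diabetic and normal patients both sit on the non-diabetic side.
- It splits the hypoglycaemia and ketoacidosis tables (SAP 7.8.1.3 and 7.8.1.4). Protocol 2.3 expects less hypoglycaemia in non-diabetic patients because they have no reason to take insulin or a sulfonylurea. The classification should not be able to place users of those drugs in that group.
- It sets the risk set for time to diabetes onset, where an already treated diabetic patient could be counted as a new case.

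**Working it through.** The plan gives no figure to reproduce, so the check sets the rules side by side. Four rules were applied: the stratum and cap rule (Protocol 3.3, 7.6), Protocol 7.3, SAP Table 9.3:1, and the onset risk set of Protocol 5.1.2. They were run on 2 × 3 × 6 = 36 constructed profiles: diabetes medication yes or no; history 'no', 'yes' or missing; six pairs of pre-treatment HbA1c values between 5.4 and 6.6. The informative profiles, with type 1 diabetes left aside, are:

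| Diabetes medication | History | HbA1c (both values) | Stratum and cap | Protocol 7.3 | SAP 9.3 | Meets 5.1.2 risk set |
|---|---|---|---|---|---|---|
| No | no | 6.0 | pre-DM | pre-DM | pre-DM | yes |
| No | no | 6.5 | DM | **Non-DM** | T2DM | no |
| No | no | 6.6 | DM | DM | T2DM | no |
| Yes | no | 6.0 | DM | **pre-DM** | **pre-DM** | **yes** |
| Yes | no | 5.4 | DM | **Non-DM** | **Normal** | no |
| Yes | missing | 5.4 | DM | **Non-DM** | T2DM (fallback) | no |
| Yes | missing | 6.0 | DM | **pre-DM** | T2DM (fallback) | yes, if missing is read as no history; no under the SAP |
| Yes | yes | 6.0 | DM | DM | T2DM | no |

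**Boundary value.** At 6.5 the Protocol 7.3 diabetes test fails (6.5 is not above 6.5). The pre-diabetes test also fails, because a value of 6.5 or more is present. The remainder class takes the patient, who then ranks below someone with 6.0. Protocol 3.3, Protocol 7.6 and SAP 9.3 all put this patient in diabetes. SAP Section 4, which lists departures from the protocol, does not mention the difference. The SAP history table records only a clarification of the diabetes definition for Section 9.3. Amendment 3 made several changes to align protocol and SAP but left this wording.

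**Treatment.** With history 'no' and HbA1c available, neither branch of the SAP fallback applies, so the IRT stratum is not consulted. HbA1c then decides alone: 5.7 to below 6.5 gives pre-diabetes and entry to the onset risk set; below 5.7 gives normal.

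**Size.** The documents do not say how many patients have such a record. For scale only, each 0.1% of randomised patients is 0.001 × 2850 = 2.85, about 3 patients, at the original sample size. At the 3600 given in SAP 9.6 it is 0.001 × 3600 = 3.6, about 4 patients.

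**The case against.** The SAP is the more detailed document, and its last revision (19 June 2020) is later than the protocol version (20 November 2019). At 6.5% it agrees with the strata, so the boundary slip changes no result if the SAP is followed. This stands; what remains is a contradiction between two governing documents that is not declared.

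The treatment gap needs an inconsistent record: a drug taken for diabetes, history entered as 'no', and every HbA1c below 6.5. Protocol 8.3.1 requires the eCRF to agree with source or the discrepancy to be explained, and the data management plan, which is not among these documents, may contain a query for it. When history is missing, the SAP fallback does carry treatment through the stratum. This also stands, and is why the number is probably small. It does not close the gap, because nothing in either document corrects such a record if it occurs.

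Using CRF and laboratory data instead of the IVRS stratum is a stated choice in SAP 7.1, so a mismatch between stratum and analysis class is not an error in itself. That is right. The fault is narrower: the analysis class can call a treated diabetic patient non-diabetic.

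Status is fixed before treatment in a randomised, double-blind trial. A few misplaced patients on one adjustment covariate should not bias the comparison between arms, and diabetes onset is exploratory. This stands too.

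**Conclusion.** Both inconsistencies are in the text and should be corrected. Severity is minor.

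The boundary error is confined to Protocol 7.3. The treatment gap is in both documents. It affects patients with medication for diabetes, history 'no' and all HbA1c below 6.5, who are stratified as diabetic and analysed as pre-diabetic or normal. It bears on the main subgroup, the hypoglycaemia and ketoacidosis splits, and one exploratory secondary endpoint. The effect on the primary hazard ratio is likely negligible. Alpha, power and the event target are unaffected. That the number is small is a judgement, resting on the inconsistency of the record needed; the documents give no count.

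A reader might infer more than the documents support:
- That patients at exactly 6.5% will be analysed as non-diabetic. Under SAP 9.3 they are type 2 diabetic.
- That these patients can enter the diabetes-onset analysis. They cannot under any version: Protocol 5.1.2, Protocol 7.3 and SAP 9.3 all bar a pre-treatment value of 6.5 or more from pre-diabetes.
- That the SAP ignores treatment altogether. Its IRT fallback can carry treatment when history is missing, or when no HbA1c exists and history is 'no'.
- That the primary result is at risk. Nothing in the documents points that way.

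**What to change.** 1. In Protocol 7.3, change the HbA1c criterion for diabetes from above 6.5 to ≥6.5, as in Protocol 3.3, Protocol 7.6 and SAP 9.3.
2. In Protocol 5.1.2, Protocol 7.3 and SAP Table 9.3:1 (T2DM row), class as diabetic any patient with antidiabetic medication for a diabetes indication at baseline, and exclude these patients from the pre-diabetes and normal classes.
3. Before unblinding, list patients with an IRT diabetes stratum, history 'no' and all pre-treatment HbA1c below 6.5, check them for recorded antidiabetic medication, and query the history entry. This profile points to treatment or to an IRT entry error, and the listing gives the count that is now unknown.
4. Record both changes in SAP Section 4.

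The cost is wording in three definitions, a note in Section 4 and one blinded listing. Step 3 is needed because the documents say that concomitant therapy is recorded (Protocol 4.2.1, 8.3.1) but do not show that its indication is, so the new criterion may not be derivable from the therapy data alone. The IRT stratum, history, HbA1c and therapy records are already held. Sample size, alpha and the testing order do not change.
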